PRECIS

Being overweight or obese can cause insulin resistance (IR), which is defined as reduced responsiveness to insulin by the cells of various tissues or organs. IR at midlife increases the risk of developing Alzheimer's disease (AD). We recently discovered novel biomarkers of brain IR (altered Tyr and Ser phosphorylated forms of insulin receptor substrate 1; IRS-1) in plasma exosomes enriched for neuronal origin. Moreover, IR is associated with AD biomarkers including deficits in resting state brain activity and cognitive performance. Calorie restriction is defined as consuming fewer calories than what is considered normal without a lack of nutrients. A certain type of calorie restriction, in which one consumes 500-600 calories a day for two consecutive days, followed by non-restricted eating for 5 days (5-2 CR), has been shown to lower peripheral insulin resistance effectively. Effects of CR and lowering peripheral IR on brain IR and cognition are unknown. The goal of this exploratory pilot study is to provide proof-of-concept that 5-2 CR at midlife can reverse brain IR, lower peripheral IR, improve cognitive performance, and increase brain activation at rest and during tasks. Specifically, we will study the effects of 8 weeks of 5-2 CR versus a control dietary intervention on brain and peripheral IR, memory and executive function, resting state default mode network activity, brain metabolism, and AD biomarkers. Forty overweight to obese women and men (between 55 and 70 years of age) will be randomized 1:1 into 5-2 CR and control groups. In the 5-2 CR group, participants will be offered "healthy living" dietary counseling at baseline, which they will be instructed to implement for five days/week. For each of the other two consecutive days/week, they will consume two shakes (Boost®, CWI Medical), providing a total of 480 Kcal/day. In the control group, participants will be offered "healthy living" dietary counseling at baseline, which they will be asked to implement for every day of the week. Participants will undergo screening including a history and physical examination, calculation of Body Mass Index (BMI, which must be ≥ 27) and a blood draw for insulin and glucose to determine whether they have insulin resistance. If participants meet eligibility criteria, they will continue with a baseline visit involving anthropometric measures, questionnaires, tests of cognitive function, brain MRI, blood draws for plasma and peripheral blood mononuclear cells, and lumbar puncture for cerebrospinal fluid biomarkers of AD. After 8 weeks, we will collect the same measures. To assess and reinforce compliance with their respective diet, participants will come into the clinic every 2 weeks to discuss compliance, measure their body weight and perform blood draws for measurement of ketones to objectively confirm energy restriction for the 5-2 CR group. We will also contact participants every week to further ensure compliance. To assess the effects of the diets on physical activity, participants will be asked to wear an accelerometer for 96 hours before and after they are on the diet.

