The study is comprised of: an initial telephone pre-screening to describe the study and inclusion/exclusion criteria to potential participants; a "Screening Visit"; randomization into one of two groups; a "Baseline Visit"; the "Outcome Visit" after 8 weeks. During the 8-week period for the 5-2 CR or control groups, participants will return every two weeks for "Compliance Visits", to assess and reinforce dietary compliance in keeping with previous protocols.^{39,40,94} The Outcome Visit will take place at the conclusion of the 8-week phase. Specifically for the 5-2 CR group, the Outcome Visit will be timed during the second of the two CR days. In total, there will be 6 outpatient visits to the NIA Clinical Unit: Screening Visit, Baseline Visit, Week 2 Compliance Visit, Week 4 Compliance Visit, Week 6 Compliance Visit, and the Week 8 Outcome Visit. There will be an additional follow-up phone call or electronic mail within 3 days of completing the Week 8 Visit to assess any problems related to their final visit. Accelerometry will be implemented on two occasions for 96 hours each time: once between the screening and baseline visits and again after the Week 8 Outcome Visit. Throughout the study, additional safety visits may take place for any clinically significant. Participants will be involved in the study for approximately 8 – 11 weeks (allowing for an up to 3 week gap between Screening and Baseline Visits). Study participation will end with completion of accelerometry after the Week 8 Outcome Visit.

It is anticipated that participants in this study will occasionally miss or fail to complete an assessment or procedure, such as a completion of a rating scale or a blood draw. Omissions such as these will be considered expected events and not protocol deviations provided they are infrequent and do not include data needed to assess safety or the primary study outcome. Cumulative proportions of these missed events in the study population will be presented to the IRB annually. In addition, the rate of omissions will be monitored by the Investigators. If an individual misses more than 15% of the required assessments/procedures or if more than 15% of the participants miss completion of the same assessment or procedure, it will be considered a deviation and a deviation report

will be sent to the IRB within two weeks.

Table 1: Procedures

Procedures	Visit 1	Visit 2		Visit 3, 4, 5	Visit 6	
		Week 0		Weeks 2, 4, 6	Week 8	

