This visit will occur within four weeks from the Screening Visit. Participants will arrive on the NIA-Clinical Research Unit after a 12-hour fast. The following procedures will be done: vital signs, anthropometric measurements (weight, waist circumference, sagittal diameter), and a blood draw for clinical labs (CBC, PT, PTT, and INR to ensure safety of the LP), urine pregnancy test (only in women who are able to become pregnant), and research labs including DNA collection (for APOE genotyping and gene expression studies). A 4-hour mixed meal tolerance test will be done. They will also have cognitive testing and will be asked to complete the Symptoms Review Questionnaire, PANAS, and RAND SF-36. A lumbar puncture (LP) will take place; up to a total of 15 mL of CSF will be collected. Participants will have a brain MRI. About 168 mL of blood will be taken during the visit. To facilitate scheduling or satisfy a given participant's request, we may split the various procedures of the Baseline Visit over two days within a week from each other.

4.d.3. 5-2 CR or control groups

At the end of the Baseline Visit, all participants will receive informational materials and one-on-one dietary counseling about "healthy living", consisting of providing and reviewing published material (by the CDC and USDA) on meal portion control, calories in common beverages, meal substitutions for controlling calorie intake, and other dietary considerations. Participants will then be randomized by study investigators into one of two groups to either 1) implement 8 weeks of 5-2 CR (cases); or 2) implement "healthy living" diet (controls).

Participants in the 5-2 group will receive all shakes (Boost®, CWI Medical) from the NIA-Clinical Research Unit.

4.d.4. Compliance visits

To assess and reinforce compliance with their respective diet, we will contact participants by phone or email (via the Secure Email & File Transfer Service: <https://secureemail.nih.gov/bds/Login.do>) at weeks 1, 3, 5, 7 and four days after the Outcome Visit. In addition, we will conduct 2, 4, and 6 week Compliance Visits. The same procedure described below will occur during each one of these.

These visits will take place during the second of the two consecutive restriction days for the 5-2 CR group or any day for the "healthy living" diet group after an 8 hour fast. A blood draw to measure β-hydroxybutyrate, vital signs and anthropometric

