Plasma ketones are strongly affected by alternate day CR acutely but not chronically;³⁹ our main objective for measuring them is to assess compliance with 5-2 CR.

We do not anticipate a change in physical activity in 5-2 CR versus “healthy living” control groups, because no change has been noted in our previous studies. Nonetheless, this is a common analysis requested by reviewers, to make sure that exercise effects did not contaminate diet effects.

The data from the gene array and DNA methylation array will be analyzed using residuals after adjustment for white blood cell differential count in linear regression models. We will take two approaches to analyze the data. First we will focus on candidate genes approach where we select specific expression probe or CpG sites; DNA for these studies will be collected during Baseline, Compliance and Outcome Visits. Second, we will run genome-wide association analysis for differences in cross sectional and longitudinal changes in gene expression or DNA methylation between the control and 5-2 CR group at each gene array probe or CpG site. DNA for genome-wide association analyses will only be collected during Baseline and Outcome Visits. For the cross sectional analyses, we will use a paired t-test at each visit, and mixed models for longitudinal analysis. In addition, we will look at overall patterns of gene expression and methylation using principle components, DIANE and hierarchical clustering tools to determine whether there are specific gene expression and methylation signature in association with 5-2 CR. As secondary analyses, we will also determine whether gene expression and DNA methylation patterns can predict the changes in metabolic, cognitive and neurochemical variables collected in this study. Within the 5-2 CR group, we will test the association between baseline levels of gene expression or DNA methylations at each probe/CpG site with longitudinal changes in the main outcome variables using mixed models.

10. b. Power analysis

The accrual number request is 100 participants. Our target sample size for completing the study is $N = 40$. There will be 20 participants in each group. We anticipate up to 60 participants will not meet inclusion criteria during the screening visit or may withdraw from the study. Enrollment will continue and withdrawals will be replaced until we have acquired complete data from 40 participants.

For power calculations, we used G*Power (<http://www.gpower.hhu.de/en.html>).

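### The array analyses name a paired t-test for two unmatched arms and give no error-rate rule for the many tests within one array (minor; primary outcome unaffected)

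*Combined protocol and SAP*

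**What the plan says.** The genome-wide part of section 10.a looks for cross-sectional and longitudinal differences "between the control and 5-2 CR group at each gene array probe or CpG site". For the first of these it says: "For the cross sectional analyses, we will use a paired t-test at each visit". The same sentence gives the longitudinal analysis to mixed models. The array data "will be analyzed using residuals after adjustment for white blood cell differential count in linear regression models".

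On allocation, the Precis says that participants "will be randomized 1:1 into 5-2 CR and control groups", and section 4.d.3 says: "Participants will then be randomized by study investigators into one of two groups". Section 10.a treats group as a between-subjects factor. Matching of participants across arms appears nowhere.

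On error rates, section 10.a sets alpha at 0.05 for every non-MRI analysis and declines to correct across the secondary outcomes because the pilot is exploratory. For fMRI it sets a voxel threshold of 0.005 and a cluster-level correction by simulation. It gives no corresponding rule for the arrays. Section 10.b quotes 80% power for a 1.5-fold expression difference (25,000 genes) and 90% power for a 40% methylation difference (45,000 CpG sites). Both use 20 per group and a two-tailed alpha of 0.05, and neither comes with an SD.

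**The concern.** A paired t-test needs a rule that links each person in one arm to one person in the other. This design has none, so two analysts with the same data could list participants in different orders and report different probes.

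The threshold raises a separate question. Declining to correct across a set of named outcomes is a declared choice. Testing tens of thousands of probes inside one outcome is a different matter, and the plan recognises that for fMRI, which is also secondary. Without a rule, nothing limits the share of chance findings in an array hit list, and section 10.a intends the study's preliminary data to inform later studies.

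**Working it through.** **Inputs.** 20 per arm, two-tailed alpha 0.05, 80% and 90% power, 25,000 genes and 45,000 CpG sites, all from section 10.b. The share s of probes that truly change is not in the documents and is assumed to be 1% to 20%.

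**1. The plan's own power.** No SD is given, so 80% and 90% cannot be reproduced directly. They can be inverted. For an unpaired t-test, power = P(T > critical t), where T is noncentral t with 38 df and noncentrality d × √(20/2) = 3.162d.
- Per-probe alpha 0.05: 80% needs d = 0.909 and 90% needs d = 1.052.
- Array-wide alpha (Bonferroni, 0.05/25,000 = 2.0e-6 and 0.05/45,000 = 1.1e-6): d = 2.076 and 2.305.

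For expression, log2(1.5) = 0.585. The implied SD is 0.585/0.909 = 0.64 log2 units per probe, or 0.585/2.076 = 0.28 array-wide. For methylation, reading 40% as percentage points (an assumption), it is 40/1.052 = 38 points or 40/2.305 = 17 points. The two readings differ more than twofold, and the text does not choose between them.

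**2. Cost of arbitrary pairing.** With unrelated partners the correlation is 0. The noncentrality is unchanged and the df fall from 38 to 19.
- At d = 0.909, power falls from 80.0% to 77.9%.
- At d = 1.052, power falls from 90.0% to 88.4%.
- Under the null, simulated type I error stays at 5.0%.

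**3. Stability of the hit list.** Simulated with 20 per arm, testing the same data under two participant orders.
- Null probes: 70.8% of the hits under the first order remain hits under the second, so about 30% drop out. New hits replace them in nearly equal number.
- True-effect probes at d = 0.909: about 95% remain, so about 5% change.

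**4. Chance hits if 0.05 is per probe and nothing differs.** 25,000 × 0.05 = 1,250 genes and 45,000 × 0.05 = 2,250 CpG sites per visit. These expected counts do not require independent probes.

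**5. False share of hits if some probes truly change.** False share = 0.05(1 − s) / [0.05(1 − s) + s × power].
- Expression, s = 1%: 0.0495/(0.0495 + 0.008) = 86%.
- Expression, s = 20%: 0.04/(0.04 + 0.16) = 20%.
- Methylation, s = 1%: 0.0495/(0.0495 + 0.009) = 85%.
- Methylation, s = 20%: 0.04/(0.04 + 0.18) = 18%.

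**6. Power at a 5% false discovery rate.** The Benjamini-Hochberg p-value cut-off c solves c = 0.05 × [(1 − s)c + s × power(c)], assuming one common d for all changed probes. The table shows power per truly changed probe.

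| s | Expression (d = 0.909) | Methylation (d = 1.052) |
|---|---|---|
| 1% | 5% | 19% |
| 5% | 21% | 44% |
| 10% | 33% | 56% |
| 20% | 46% | 68% |

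**The case against.** **Paired could mean baseline against outcome within a person.** The wording does not allow this. The analysis is cross-sectional, is run at each visit, contrasts the arms, and leaves change over time to mixed models. The word may be a slip that an analyst would correct, but the plan should not depend on that.

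**Pairing does little harm.** This largely stands. The error level is kept, about 2 points of power are lost, and most true-effect hits survive re-ordering. A reader might infer that the whole list is arbitrary or that false positives are inflated. The calculations support neither. The instability is mainly among chance hits.

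**Multiplicity was addressed.** It was, in part. Section 9 calls all secondary outcomes exploratory, and section 10.a waives correction across them. Whether that waiver reaches the tests inside one array is a matter of interpretation, so the defect is an unclear scope. The 0.05 in section 10.b may also be meant array-wide, in which case the 1,250 and 2,250 counts do not apply.

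**Sidedness.** A reader might infer a conflict between the one-tailed t-tests of section 10.a and the two-tailed array power. The one-tailed sentence closes the paragraph on scalar measures, and two-tailed is the only sidedness stated for the arrays. It is enough to repeat it in section 10.a.

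**Candidate probes.** A reader might want a chance count for these over all visits. The plan gives no set size. It says "DNA for these studies will be collected during Baseline, Compliance and Outcome Visits", which describes sampling and does not say that each visit is tested, so no count is supported.

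**Conclusion.** Both parts hold, at minor severity.

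- **The paired t-test is wrong as written** for two independently randomised, unmatched arms. The consequence is a test that is undefined without invented pairs, a loss of about 2 points of power, and a hit list that partly depends on participant order.
- **No error-rate rule covers the tests within one array.** The chance counts in step 4 and the false shares in step 5 hold only if 0.05 is per probe. The false shares also assume that 1% to 20% of probes change and that the stated power holds for each changed probe.

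The documents do not show that the stated 80% and 90% are wrong. They show that these figures cannot be checked without an SD and a statement of what 0.05 refers to. The primary outcome is unaffected.

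**What to change.** **(a) Test.** In section 10.a, replace the paired t-test with a two-sided unpaired comparison of the arms, adjusted for the white-cell differential counts already planned. Preferably fit one linear model with group and the cell counts together, and list the counts used. The one-step fit is a preference; the unpaired test is the necessary correction. Repeat the two-tailed alpha in this paragraph.

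**(b) Threshold.** State a 5% Benjamini-Hochberg false discovery rate within each genome-wide array contrast. Limit the no-correction sentence to comparisons across outcomes. Nominal ranked lists can stay if they are labelled exploratory.

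**(c) Power.** In section 10.b, say whether 0.05 is per probe or array-wide. Restate the array power, or the detectable difference, at the chosen threshold, with the SD.

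**Cost.** Wording and standard software, with no added samples, visits or participants. The real downside is fewer nominal hits and lower stated array power, as the table in step 6 shows under its assumptions.

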19. To assess the effects of the two diets on methylation patterns in genes of candidate CR pathways;
20. To assess the effects of the two diets on global methylation patterns in PBMCs.

2.a. Primary objectives

Primary objective is to demonstrate that 8-weeks of 5-2 CR plus “healthy living”

counseling in a group of overweight, late middle-aged to aged participants will significantly increase the ratio of plasma exosomal p-panY-IRS-1 to p-S312-IRS-1, compared to baseline and to controls who only receive “healthy living” counseling.

2.b. Secondary objectives

Secondary objectives are noted under specific aims 5-21. Collectively, we aim to demonstrate that 8-weeks of 5-2 CR plus “healthy living” counseling in a group of overweight, late middle-aged to aged participants will significantly improve peripheral insulin sensitivity, decrease fMRI activation in meso-cortico-limbic areas involved in appetitive food salience and reward pathways, increase intrinsic functional connectivity of the DMN, improve brain metabolism, AD biomarker profile and cognitive performance compared to baseline and controls who only receive “healthy living” counseling.

3. Subjects

3.a. Description of study population

The study population will consist of overweight, older (55-70 years old), men and women with evidence of IR and central obesity. The requirement for IR was set because it defines a population at increased risk for AD,⁸⁹ and IR may be responsive to brief³⁹ or extended⁹⁰ CR in overweight human participants. The upper and lower age limits were set because we are interested in the effects of IR and of 5-2 CR on the preclinical phase of AD, at midlife, 15-20 years prior to the onset of clinical disease.

The accrual target is 100 participants to allow for 40 participants that will be successfully enrolled and complete the study and 60 screen failures and withdrawals. Withdrawals will be replaced.

3.b. Inclusion criteria

1. BMI \geq 27; in addition, weight \leq 350 lbs (weight limit for MRI scanner);
2. Age of 55-70 years;
3. HOMA-IR \geq 1.8;
4. MMSE \geq 26

3.c. Exclusion criteria

1. History of cardiovascular disease;
2. History of clinically significant stroke or other neurological disease of the central nervous system;
3. History of substance abuse in the past 6 months or positive urine drug screen;
4. History of clinically significant endocrine disorders (common mild endocrine

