disorders, such as untreated subclinical hypothyroidism with TSH < 10 mU/l or successfully treated hypothyroidism may be allowed);

- 5. History of eating disorders, significant GI disorders or malabsorption disorders;
- 6. History of type 2 diabetes; and/or use of anti-diabetes medications or insulin; and/or type 2 diabetes diagnosed during the screening visit based on fasting glucose > 125 mg/dL;
- 7. History of hypoglycemia; and/or a fasting glucose < 70 mg/dL during the screening visit.
- 8. Current use of systemic corticosteroids;
- 9. Positive screening tests for HIV, HCV or HBV;
- 10. Hematocrit less than 35% or hemoglobin less than 11 mg/dL;
- 11. ALT or AST > 1.5 times the upper normal limit;
- 12. Contraindications for MRI (pacemakers, ferrous metal implants or shrapnel in or around the head, etc.).
- 13. Contraindications to LP, such as Coumadin, coagulopathy (international normalized ratio, or INR > 1.5; prothrombin time (PT), partial prothrombin time (PTT) > 1.5 x upper normal limit). Aspirin 81 mg qd is allowed. Aspirin up to 325 mg qd is allowed, if withheld for 7 days prior to the LP.
- 14. Pregnancy or nursing.
- 15. Refusal to consent to genetic testing for APOE.

4. Study Design and Methods

4.a. Study overview

This study is a randomized clinical trial, where participants will be assigned into two groups. In the 5-2 CR group, participants will be offered “healthy living” dietary counseling at baseline, consisting exclusively of published literature from the CDC and USDA, which they will be instructed to implement for five days/week. In addition, they will be instructed to consume only two shakes (Boost®, CWI Medical) providing a total of 480 Kcal/day for two consecutive days/week. In the control group, participants will be offered “healthy living” dietary counseling at baseline, which they will be instructed to implement for every day of the week.

Should a participant not be able to keep their scheduled study visits due to an unforeseen circumstance, and they are on 5-2 CR, she or he may be asked to implement CR on another day, or to extend the 5-2 CR diet for an additional week. Voluntary dropouts will be replaced until we have acquired complete data from 40 participants.

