No major adverse effects have been associated with mild to moderate intermittent calorie restriction.^{39,40,94} Two of our previous CR studies did not have a reported serious AE incident.^{39,40} More severe caloric restriction in humans relative to our studies also produced no serious AEs⁹⁴. We classify the 5-2 CR and control diet as minimal risk.

8. Subject safety monitoring

8.a. Monitoring of Subjects

The investigator or clinical staff performing a study procedure will monitor subject safety. This includes physicians, licensed practitioners (NPs) and RNs during LPs, blood draws, mixed meal testing, and History and Physical sessions; investigators administering questionnaires and cognitive testing, MRI techs and investigators during MRIs.

The PI will make determinations regarding the presence and grading of on adverse events (AEs) and unanticipated problems (UPs). Whenever study investigators contact subjects throughout the study, they will seek information on AEs and UPs. AE's and UPs will also be elicited during study visits, by subjects filling in the symptoms review questionnaire or during history and physical examination. Participants will be asked to use electronic mail (Secure Email & File Transfer Service: <https://secureemail.nih.gov/bds/Login.do>) or telephone to inform the investigators about any AE's or UPs experienced. AEs and UPs may be observed by the Investigator and/or study staff, elicited from the subject and/or family member, or volunteered by the study subject. AEs and UP's that had previously been reported by study subject will also be reassessed for duration, intensity and

possible reoccurrence. Assessment of safety will include vital signs, history and physical sessions, questionnaires on physical and psychological symptoms and clinical labs as indicated. Any AE or UP that occurs between the times a study participant signs the informed consent form and the end of participation will be assessed and recorded under NIH HRPP SOP # 16 and 16 A.

In particular, we will monitor the weight loss of the participant. If a participant on 5-2 CR loses 4-5% of their body weight within a 2-week period between visits, additional safety visits will be scheduled every week to monitor body weight more closely. If weight loss in that range or greater continues to occur, participants will be removed from the study.

A study participant will also be discontinued from the study if:

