- Any adverse event occurs Grade 2 or greater and possibly related to the study.
- The participant develops any of the exclusion criteria.
- There is persistent non-compliance with study requirements (keeping follow-up visits).

Participants will be informed about new information from this or other studies that may affect their health, welfare, or willingness to stay in this study. Participants may decide to stop participating at any time. Any data or blood collected until that point in time will remain part of the study and are the property of the National Institute on Aging.

9. Outcome measures

All secondary outcome variables in this pilot study are exploratory.

9. a. Primary outcome measures

- Exosomal p-S312-IRS-1/p-panY-IRS-1 ratio

9. b. Secondary outcome measures

- Other exosomal protein and mRNA biomarkers of AD;
- S_I and HOMA-IR, indices of insulin resistance, derived from insulin and glucose values taken from a fasting blood draw;
- fMRI activation to appetitive food versus non-appetitive food stimuli;
- Resting state fMRI intrinsic functional connectivity of DMN;
- Behavioral performance and fMRI activation during a Color-Word Stroop task;
- Brain metabolites assessed with Magnetic Resonance spectroscopy and regional perfusion assessed with arterial spin labeling;
- Memory and executive function scores.
- Anthropometric measures (weight, waist circumference, sagittal diameter);

- Clinical Labs: lipid panel, uric acid;
- Plasma ketones, such as β -hydroxybutyrate and other metabolites.
- Plasma metabolites and hormones (GLP-1, insulin) during a mixed meal test;
- CSF and plasma AD biomarkers, including $\text{A}\beta_{1-42}$ and p_{181}Tau ;
- Plasma and CSF neurotrophic factors, such as BDNF;
- Plasma and CSF reactive oxygen species, advanced glycation end-products and advanced oxidation protein products;
- Plasma and CSF pro-inflammatory cytokines, such as IL-6, IL-8, IL-12 and IL-23;
- Ratings of symptoms that can occur with 5-2 CR, mood and quality of life changes, recorded during both the 5-2 CR and control diet phases;
- Physical activity measured using an accelerometer.
- Global gene expression pattern, mitochondria gene expression and expression of other gene pathways responding to CR
- Genome-wide methylation in peripheral blood mononuclear cells

10. Statistical Analysis

10. a. Analysis of data/study outcomes

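### Participants removed after randomisation are in effect replaced until 40 have complete data, with no Week 8 primary-outcome sample and no stated analysis set; the expected bias is small and the remedy cheap

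*Combined protocol and SAP*

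**What the plan says.** **Replacement.** Section 10.b: "Enrollment will continue and withdrawals will be replaced until we have acquired complete data from 40 participants". Section 3.a: "Withdrawals will be replaced". Section 4.a is narrower in whom it names: "Voluntary dropouts will be replaced until we have acquired complete data from 40 participants".

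**Removal.** Section 4.d.3 randomises at the end of the Baseline Visit (the list in 4.d.1 places it before that visit), so every removal on the diet comes after randomisation. Section 8.a schedules weekly safety visits "If a participant on 5-2 CR loses 4-5% of their body weight within a 2-week period between visits", and adds: "If weight loss in that range or greater continues to occur, participants will be removed from the study". It also discontinues a participant when "Any adverse event occurs Grade 2 or greater and possibly related to the study", when "The participant develops any of the exclusion criteria", or for persistently missed visits.

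**Analysis.** Section 8.a keeps data and blood already collected. Section 10.a specifies a REML mixed model with Group, Time (Baseline and Outcome only) and their interaction. It names no analysis set and no method for missing outcomes. No early-termination visit or Week 8 sample is described for those removed.

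**Expected weight loss.** Section 4.a.2 expects about 2% per week on 5-2 CR. The Introduction reports about 8% of baseline weight over 8 weeks of alternate-day restriction, citing the same reference. The control-condition rationale in Section 4.a.1 cites 6.5 kg over 8 weeks of 5-2 CR, from another reference.

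**The concern.** Enrolling until 40 people have complete data restores the count but not the missing Week 8 values. The Week 8 comparison then rests on those who were not removed, and one removal rule applies to a single arm and depends on response to the diet. Randomisation no longer fully protects that comparison, and a reader cannot tell whether the estimate describes everyone assigned to 5-2 CR or only those who finished it. This matters even in a pilot: the primary objective is a between-group demonstration, and Section 10.a offers the data as a basis for future studies.

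A separate documentation matter concerns the weight rule. On the Section 4.a.2 expectation, an average compliant participant loses close to the amount that triggers extra safety visits in Section 8.a. On the other two figures, the average loss is about half of that.

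**Working it through.** **1. The plan's own power.** Inputs from Sections 10.a and 10.b: f = 0.3, N = 40 (20 per group), m = 2 time points, correlation 0.4, alpha 0.05 one-tailed.

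- Noncentrality = f² × N × m / (1 − 0.4) = 0.09 × 40 × 2 / 0.6 = 12.0.
- Implied difference in change = √(4 × 12 / 40) = 1.095 SD of change.
- Standard error of that difference = √(2/20) = 0.316 SD of change.
- Power: one-tailed t on 38 df with noncentrality 1.095/0.316 = 3.46 gives 0.96. The F test at 0.05 gives 0.92.

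The plan's figure of over 90% is reproduced for 40 completers.

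**2. How many the weight rule might remove (assumed).** The documents give no rate. Take a mean loss of about 2% per two weeks (the Introduction's 8% in 8 weeks), and read continued loss as at least 4% in one pair of consecutive two-week intervals. With an assumed SD of 1.0 to 1.5 percentage points and a correlation between intervals of 0 to 0.5, between 0.05% and 2.8% are removed. I use 3%. Counting more than one pair of intervals would raise the top of this range, so 5% is also shown in step 4.

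**3. Bias at 3% removed.** Assume the greatest weight losers in the 5-2 CR arm lose their Week 8 value, and that weight loss correlates 0.3 to 0.5 with improvement in the ratio. With unit SD at each visit:

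- Variance of change = 2 × (1 − 0.4) = 1.2. Variance of Week 8 given baseline = 1 − 0.4² = 0.84. Their ratio is 0.70.
- Shift in mean weight loss among those kept = φ(1.881)/0.97 = 0.0680/0.97 = 0.0701 SD.
- Lower end (correlation 0.3 with total change; the model, using all baselines, leaves 0.70 of the shift): 0.3 × 0.0701 × 0.70 = 0.015 SD of change.
- Upper end (correlation 0.5 with the part of Week 8 independent of baseline): 0.5 × 0.0701 × √0.70 = 0.029 SD of change.

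A simulation of 4,000,000 participants gives the same two values.

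**4. Size.**

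| Quantity | Lower | Upper |
|---|---|---|
| Bias, SD of change | 0.015 | 0.029 |
| As share of 1.095 | 1.3% | 2.7% |
| In standard errors (÷ 0.316) | 0.05 | 0.09 |
| One-tailed power (0.96 without bias) | 0.956 | 0.952 |

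At 5% removed, the shift is φ(1.645)/0.95 = 0.109, and the same steps give 0.023 to 0.045 SD, at most 0.14 standard error. At 3%, extra participants needed for 20 completers on 5-2 CR = 20/0.97 − 20 = 0.6.

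**5. Weight-loss figures side by side.**

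| Source | Stated | Over 8 weeks | Per 2 weeks |
|---|---|---|---|
| Section 4.a.2, 5-2 CR | about 2% per week | 1 − 0.98⁸ = 14.9% | 1 − 0.98² = 3.96% |
| Introduction, alternate-day, same reference | about 8% in 8 weeks | about 8% | about 2% |
| Section 4.a.1, 5-2 CR | 6.5 kg in 8 weeks | 6.2% to 8.7% at an assumed 105 to 75 kg | about 1.5% to 2.2% |

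The Section 8.a trigger is 4-5% in two weeks.

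**The case against.** The strongest reply is that this is an exploratory pilot, the likely bias is trivial, and the plan already handles part of it. Data already collected are kept, REML can use baseline records, Section 4.d.1 has missed assessments monitored and reported to the IRB, and the effect in those who complete the diet is a legitimate target for proof of concept. Most of this stands and sets the weight of the point. It does not supply Week 8 values. On-diet weight loss and symptoms are not in a two-visit model, so the model cannot correct for removals they cause. If the completer effect is the target, the plan should say so.

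It is also fair that replacing investigator-removed participants is an inference, since Section 4.a names voluntary dropouts. The inference follows from enrolling until 40 have complete data.

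A reader might go further in three ways that the documents do not support:

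- **That up to 15% of the 5-2 CR arm would be removed.** Section 7.p's 9-15% refers to adverse events described as minor. Removal requires Grade 2 or greater and possible relatedness, and that rate says nothing about the weight rule.
- **That the average compliant participant would be removed.** The first trigger leads only to closer monitoring. Removal needs continued loss, only the Section 4.a.2 figure brings the average near the trigger, and nothing says the trigger was derived from any of these figures.
- **That the energy-restriction figure in Section 4.a.1 and the body-fat figure in Section 10.b add to the weight conflict.** They measure different quantities, and no contradiction with them is shown.

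**Conclusion.** The point holds as a cheap improvement with a small expected effect. Followed as written, the plan yields something close to a completer comparison under a partly arm-specific removal rule, without saying so. The net direction is unknown: if weight loss tracks improvement, the weight rule understates 5-2 CR, while removals for adverse events, new exclusion criteria or missed visits could act either way. The weight-rule bias of under 0.1 standard error rests on the assumed 3% removal and correlation of 0.3 to 0.5. It would be wrong to conclude that the sample size is inadequate or the power claim mistaken.

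The weight-loss discrepancy is a separate and narrower finding: about 15% against about 8% over 8 weeks from one reference (for different regimens), with the 6.5 kg figure close to the latter.

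**What to change.** 1. Separate stopping the diet from leaving follow-up. Invite those who stop, where they consent and the investigator judges it safe, to the already scheduled Week 8 fasting blood draw for the primary outcome. This is the step that matters most, because changing the analysis set without new Week 8 values alters little.
2. Make all randomised participants, in their assigned group, the primary analysis, with completers as a sensitivity analysis. Replacements are added to those removed and do not displace them.
3. Report removals and replacements by arm and reason.
4. Separately, reconcile the weight-loss statements in the Introduction and Sections 4.a.1 and 4.a.2 with each other and with the Section 8.a trigger. No figure or threshold is proposed here.

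The cost is amendment wording and a few blood draws. The estimate moves somewhat toward the effect of being assigned to 5-2 CR, and the sensitivity analysis keeps the completer view. Participants who persistently miss visits may not attend the Week 8 draw either, so the first step will not recover everyone.
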